1.1 Clinical Studies

[figure not shown]
The safety, pharmacokinetics (PK), and pharmacodynamics (PD) of SKI-O-703 have been evaluated in 2 clinical studies, a single ascending dose clinical study (OSCO-P1201) and a multiple ascending dose clinical study (OSCO-P1202) in healthy subjects.

In Study OSCO-P1201, single oral doses of SKI-O-703 ranging from 50 to 800 mg were generally safe and well tolerated by the healthy male and female subjects. There were no deaths, serious adverse events (SAEs), or treatment-emergent adverse events (TEAEs) that led to discontinuation of the study. Ten of 48 subjects (20.8%) reported a total of 18 TEAEs; of these, 3 TEAEs were reported by 3 subjects (25.0%) after receiving placebo and 15 TEAEs were reported by 7 subjects (19.4%) in the SKI-O-703 treatment groups. There were no dose-dependent trends noted in the TEAEs reported. The most commonly reported TEAE was headache, which was reported by 3 subjects (8.3%) who received SKI-O-703 and 1 subject (8.3%) who received placebo. All TEAEs across the 50 mg to 600 mg dose range were considered mild in intensity; 6 treatment-related moderate-intensity TEAEs, reported in 2 subjects, occurred at the highest dose of 800 mg SKI-O-703. All TEAEs were resolved by the end of the study. All individual hematology and coagulation, serum chemistry, and urinalysis values outside of the reference ranges were considered not clinically significant by the investigator. No TEAEs related to laboratory parameters were reported.

In Study OSCO-P1202, multiple oral doses of SKI-O-703 200 mg once daily (QD), 400 mg QD, and 200 mg twice daily (BID) were safe and well tolerated by the healthy male and female subjects. There were no deaths or SAEs; however, 1 subject reported TEAE of back pain that led to discontinuation of 200 mg SKI-O-703 BID. Overall, 7 subjects (29.2%) reported a total of 17 TEAEs; of these, 2 subjects (33.3%) reported 6 TEAEs after receiving placebo and 5 subjects (27.8%) reported 11 TEAEs after receiving SKI-O-703. The most commonly reported TEAEs were nausea and headache, each were reported by 2 subjects (33.3%) in the 200 mg SKI-O-703 BID treatment group and by 1 subject (16.7%) in the placebo group. All TEAEs were considered mild or moderate in intensity, and both moderate TEAEs occurred in the placebo group. Except for 1 subject who reported ongoing TEAEs of pyuria and chlamydial infection, all TEAEs were resolved by the end of the study. No

apparent treatment- or dose-related trends were observed in clinical laboratory values, physical examination findings, or 12-lead electrocardiogram (ECG) results. There was a slight trend in the mean increase of systolic blood pressure from baseline in the 200 mg BID group at Days 16 and 21, and diastolic blood pressure values at Days 16 and 21 also demonstrated a slight trend of a mean increase for all doses of SKI-O-703. There were no significant changes in systolic and diastolic blood pressure for all doses of SKI-O-703 versus placebo at Days 16 and 21.

1.2 Nonclinical Studies

Oscotec Inc.

SKI-O-703

Protocol: OSCO-P2101 Version 4.0 (Amendment 3)

22 April 20

1.3 Dose Rationale

SKI-O-703 was safe and well-tolerated in healthy volunteers when administered as single ascending doses over the dose range of 50 to 800 mg (Study OSCO-P1201), and multiple ascending doses at 200 mg QD, 400 mg QD and 200 mg BID for 7 days (Study OSCO-P1202). Based on the safety data from the various doses administered in these studies, there are no specific considerations that would concern the use of SKI-O-703 at doses proposed in this Phase 2 study.

Following multiple ascending doses of SKI-O-703 at 200 mg QD, 400 mg QD, and 200 mg BID (Study OSCO-P1202), a reduction in the PD endpoint “percentage of basophils expressing CD63+” was observed in healthy volunteers; on average, CD63+ expressing basophils were suppressed by 95%, 99% and 86% at steady state (Day 7) following administration at 200 mg QD, 400 mg QD, and 200 mg BID, respectively. Thereafter, the suppression of basophils expressing CD63+ was maintained at -72% or below for up to 2 and 8 hours following once-daily dosing at 200 mg and 400 mg, respectively, and up to 12 hours (ie, over a full 24-hr period) following twice-daily dosing at 200 mg. As the PD effect was sustained for longer after twice-daily dosing compared to once-daily dosing, twice-daily dosing at 200 mg and 400 mg has been selected.

As 400 mg BID has not been studied previously in humans, exposure (C_{max} and $AUC_{0-\tau}$) to SKI-O-592, M2, and M4 following 400 mg BID dosing has been estimated based on data observed previously at different dose levels. To ensure that predictions are cautious and

robust, steady-state C_{max} and $AUC_{0-\tau}$ following 400 mg BID have been predicted in 2 ways using data from Study OSCO-P1202:

1. AUC_{0-12} (400 mg, Day 1) \times Accumulation Ratio (200 mg BID)

2. PK Parameter (200 mg BID, Day 7) \times 2

Systemic exposure (C_{max} and $AUC_{0-\tau}$) to SKI-O-592, M2, and M4 at 400 mg BID is predicted to be higher using the second approach [PK Parameter (200 mg BID, Day 7) \times 2]. For SKI-O-592, C_{max} and $AUC_{0-\tau}$ are predicted to be 6160 ng/mL and 14600 h ng/mL, respectively, and for M2 C_{max} and $AUC_{0-\tau}$ are predicted to be 994 ng/mL and 10000 h ng/mL, respectively, which is well within exposure levels calculated at the NOAEL in rats, and comparable to levels previously observed at 800 mg in Study OSCO-P1201. However, due to the very low M4 metabolite ratios observed in rats compared to healthy volunteers, predicted exposure to M4 (644 ng/mL and 1970 h ng/mL for C_{max} and $AUC_{0-\tau}$, respectively) is higher than the NOAEL exposure. Therefore, the dosing regimens proposed for this study (200 mg BID and 400 mg BID) have been carefully selected to ensure that exposure to M4 does not exceed levels observed previously in healthy volunteers (Study OSCO-P1201, 800 mg).

*Note: Because increases in systemic exposure to M4 were less than proportional to the dose of SKI-O-703 in Studies OSCO-P1201 and OSCO-P1202, and a reduction in M4 levels was observed over time in Study OSCO-P1202, both means of estimating C_{max} and $AUC_{0-\tau}$ for M4 at 400 mg BID are considered to be cautious approaches, potentially overestimating exposure at 400 mg BID. An interim safety and PK data review will be performed by the DMC for the first 5 subjects dosed (including 2 subjects dosed with 400 mg BID) before the remaining subjects are treated.

Following single oral administration of 400 mg SKI-O-703 (Study OSCO-P1203), overall systemic exposure to SKI-O-592, M2 and M4 (AUC_{0-t} and $AUC_{0-\infty}$) was comparable between the fed and fasted state, with 90% CI for the ratio (Fed / Fasted) contained entirely within the BE limits (0.80, 1.25) for SKI-O-592 and M4. By contrast, when administered in the fed state there was an approximate 56%, 43% and 46% reduction in maximum exposure (C_{max}) for SKI-O-592, M2 and M4, respectively, with an associated 2.5 to 4 hours delay in median T_{max} across all analytes. Since the overall extent of absorption is unaffected by the intake of food, but peak exposure is reduced, dosing is recommended with food in this

Phase 2 study to reduce the potential for AEs which may be associated with spikes (i.e. high C_{max}) in SKI-O-592, M2 and M4.

1.4 Placebo Rationale

The proposed study is a double-blind, placebo-controlled, randomized trial of two doses of oral SKI-O-703 for patients with persistent and chronic ITP. Subjects will be allowed to receive stable doses of background medications including corticosteroids and immunosuppressive drugs, in line with the current standard of care. Any subject who cannot adhere to the protocol or who discontinues treatment will have an end-of-treatment visit and will be followed for the intended duration of the study.

1.5 Benefits and Risks Assessments

In the clinical development program, the safety, tolerability, and PK of SKI-O-703 have been evaluated in 2 clinical studies, a single ascending dose clinical study (OSCO-P1201) and a multiple ascending dose clinical study (OSCO-P1202) in healthy subjects. No deaths and SAEs were reported in these studies; however, 1 subject reported TEAE of back pain that led to discontinuation of SKI-O-703. All adverse events (AEs) were mild to moderate in intensity.

As described in [Section 1.2](#), SKI-O-703 was efficacious in preventing thrombocytopenia induction in an anti-CD41 antibody induced murine ITP model.

There are no important identified risks with SKI-O-703. The identified potential risks associated with SKI-O-703 included immune system effects, gastrointestinal effects, liver enzyme changes, cardiovascular effects, and headache.

Gastrointestinal effects and headache have been observed clinically, while immune system effects, liver enzyme changes, and cardiovascular effects are considered important potential risks based on non-clinical data and the SKI-O-703 mechanism of action. Considering the measures to minimize the risks to patients participating in the SKI-O-703 clinical development program, and the nonclinical and clinical evidence highlighted above, the benefits of the conduct of the proposed clinical study outweigh the associated risks.

2 Study Objectives

2.1 Primary Objective

To evaluate the safety and efficacy on the primary endpoint (platelet response) of select (200 mg BID and 400 mg BID) doses of SKI-O-703 compared to placebo in patients with persistent and chronic ITP, with a platelet count <30,000/ μ L on 2 occasions at least 7 days apart with the confirmatory count being taken during Screening.

2.2 Secondary Objectives

The secondary objectives of this study are as below:

- To evaluate the efficacy on the secondary endpoints of select (200 mg BID and 400 mg BID) doses of SKI-O-703 compared to placebo in patients with persistent and chronic ITP
- To investigate the PK profile of SKI-O-592 (the free base of SKI-O-703) and its metabolites (M2 and M4) in patients with persistent and chronic ITP
- To evaluate the effects of SKI-O-703 on PD biomarkers in patients with persistent and chronic ITP.

2.3 Exploratory Objectives

The exploratory objectives of this study are as below:

- To evaluate the PK/PD relationship between plasma concentrations of SKI-O-592, M2, and M4 and the percent change in activated CD63+ basophils in peripheral blood in patients with persistent and chronic ITP
- To evaluate the changes of the exploratory endpoints of select (200 mg BID and 400 mg BID) doses of SKI-O-703 compared to placebo.

[figure not shown]
3 Investigational Plan

3.1 Study Design

This is a randomized, double-blind, multicenter, placebo-controlled, parallel dose study to evaluate the efficacy, safety, tolerability, PK, and PD of select (200 mg BID and 400 mg BID) doses of SKI-O-703 in persistent and chronic ITP patients who have failed to respond or relapsed after prior therapy, with a platelet count $<30,000/\mu\text{L}$ on 2 occasions at least 7 days apart with the confirmatory count being taken during Screening (the most recent result from the central laboratory will be considered as the confirmatory platelet count, when an unscheduled visit(s) is performed during the screening period).

[figure not shown]
A minimum of 60 subjects are planned to enroll in 3 treatment groups (24 subjects in each of the active treatment groups and 12 subjects in the placebo group). Subjects will be randomly assigned to the 3 groups using a 2:2:1 ratio to receive one of the 2 select doses of SKI-O-703 or placebo. First 5 subjects randomly assigned in the study will have the safety run-in period for the first 1 week with interim safety and PK assessments on Day 8 (± 2 days). Subjects in the safety run-in period will continue to be dosed whilst the interim analysis is being conducted. However, further enrollment in each treatment group will only resume after safety and PK data of the first week for the first 5 subjects are reviewed and considered satisfactory by the Data Monitoring Committee (DMC). A subset of at least 20 subjects, who are not included in the safety run-in period, will be randomized to undergo PK/PD assessments at a selected number of sites. Randomization will be stratified to balance subjects with respect to prior TPO-receptor agonist use (yes/no) and degree of baseline thrombocytopenia (ie, baseline platelet count $<$ or $\geq 15,000/\mu\text{L}$). A schematic diagram of the overall study design is presented in [Figure 1](#) and [Figure 2](#).

Figure 1 **Study Design Schematic (for the First 5 Subjects in the Safety Run-in Period only)**

Abbreviation: BID, twice daily

Note: First 5 subjects randomly assigned in the study will have safety run-in period for the first 1 week with interim safety and PK assessments on Day 8 (± 2 days). Subjects in the safety run-in period will continue to be dosed whilst the interim analysis is being conducted. However, further enrollment in each treatment group will only resume after safety and PK data of the first week for the first 5 subjects are reviewed and considered satisfactory by the Data Monitoring Committee.

Figure 2**Study Design Schematic (For Subjects Other Than Enrolled in the Safety Run-in Period)**

Abbreviation: BID, twice daily

Screening Period

The study will include up to 4 weeks of screening period. All potential subjects will sign and date the informed consent form (ICF) prior to any study assessments or procedures. These subjects will be assessed as per the eligibility criteria at Screening. After completing all screening assessments, subjects who meet all the inclusion and none of the exclusion criteria will proceed to the treatment period.

12-week Treatment Period

- *1-week Safety Run-in Period (for the first 5 subjects only):* First 5 subjects randomly assigned in the study will have the safety run-in period for the first 1 week with interim safety and PK assessments on Day 8 (± 2 days). Subjects in the safety run-in period will continue to be dosed whilst the interim analysis is being conducted. However, further enrollment in each treatment group will only resume after safety and PK data of the first week for the first 5 subjects are reviewed and considered satisfactory by the DMC.

For all subjects, on Day 1, subject's eligibility will be confirmed and baseline safety evaluations will be performed (ECG, physical examination, vital sign measurements, and safety laboratory assessment). Eligible subjects will be randomly assigned to receive either one of the doses of SKI-O-703 or placebo. On Day 1, the investigative site staff will administer the morning dose. The evening dose of study medication will be administered 12 hours after the morning dose. Subjects will be administered the study medication with enough water to swallow the capsule. The study medication will be taken no later than 30 minutes after food.

After dosing, all subjects will be subjected to safety assessments and a subset of at least 20 subjects, who are not included in the safety run-in period, will be subjected to PK and PD assessments according to the Schedule of Events ([Table 2](#)). Subjects enrolled in the safety run-in period will be admitted for 24 hours on Days 1, 8, and 84 or 85 of the study. Subjects selected for the PK/PD portion of the study will be admitted for 24 hours on Days 1 and 84 or 85 of the study.

The maximum duration of study participation for a subject will be 20 weeks, which consists of up to 4 weeks of screening period, 12 weeks of treatment period, and 4 weeks of follow-up period.

3.1.1 Dose Interruption and Reduction

It is recognized that some AEs may require dose adjustment or study drug discontinuation. Intra-subject dose reduction or escalation is permitted and based upon treatment-related adverse events observed ([Table 1](#)).

After experiencing an AE, subjects whose laboratory results return to baseline values and remain stable for 4 consecutive weeks have the option to increase the dose of SKI-O-703 1 dose level up to the randomized dose level.

Table 1 Guidelines for Dose Interruption or Reduction^a

AE	Occurrence	Action
ALT elevations (range 3 to 5 \times ULN) Alkaline Phosphatase > 3 \times ULN and > 2 \times baseline	First	
 If asymptomatic (no nausea, anorexia, vomiting), repeat test within 72 hours^b and, if stable or lower, may continue dosing of study drug. If on repeat test value has increased further but remains < 5 \times ULN and asymptomatic, withhold study drug and retest weekly until values becomes stable. When stabilized to < 5 \times ULN, continue dosing with the study drug. If symptomatic or > 5 \times ULN, withhold study drug. Follow the subject weekly until symptoms abate and values return to baseline per confirmation from central laboratory; at which time study drug may be restarted at a 50% reduced dose by taking only one daily dose. 
Note: Discontinue study drug permanently if the ALT elevation is accompanied by an elevation in direct bilirubin to > 2 mg/dL (34.2 mmol/L).

	Second	Discontinue study drug permanently.
ANC <1,000/mm ³ or febrile neutropenia	First	Withhold dose until ANC \geq 1000/mm ³ , or has returned to baseline, then reduce the dose by skipping one of the daily dose and increase to previous dose if ANC remains stable for 2 weeks on reduced dose.
	Second	Discontinue study drug permanently if the intolerance reoccurs or persists.
Sustained increased systolic (> 160 mmHg) or sustained increased diastolic (> 100 mmHg) blood pressure in a previously normotensive subject	First	
Study drug may be withheld for 5 to 7 days and then restarted at a reduced dose by skipping one of the daily dose.
 
Irrespective of study drug dose adjustment, subjects who develop a sustained increased systolic (>140 mmHg) or a sustained increased diastolic (>90 mmHg) blood pressure should be started on antihypertensive medications (e.g. lisinopril 5mg daily) or have their antihypertensive regimen adjusted if already on any antihypertensive agent.

	Second	Discontinue study drug permanently if the hypertension reoccurs or persists.
Intolerable nausea or vomiting (see Section 5.8.2 for further details)	First	Study drug may be withheld for 5-7 days and then restarted at a reduced dose by skipping evening dose.
	Second	Discontinue study drug permanently if the intolerance reoccurs or persist.

AE	Occurrence	Action
QTcF >500 ms for female subject OR >480 ms for male subject, at any time point	-	
The ECG should be repeated as triplicate (all three within 2 minutes) and a cardiology consult may be obtained as medically necessary.
 
 • If the repeat ECG confirms QTcF >500 ms (females) or >480 ms (males), dosing must be interrupted for up to 14 days • If the QTcF resolves to ≤480 ms (males and females)/they may resume dosing at the reduced dose by skipping one of the doses (ie, morning or evening) • If the QTcF remains >480 ms (males and females) after 14 days of dose interruption, the study drug must be permanently discontinued.
QTcF change of >30 ms from baseline	-	If the QTcF has increased >30 ms when compared to the baseline with no other known etiology, and the principal investigator considers it clinically significant then a confirmatory ECG (single) will be performed and dose should be reduced by skipping one of the doses (ie, morning or evening) for the remainder of the study.

Abbreviations: ACE, angiotensin-converting-enzyme; AE, adverse event; ALT, alanine aminotransferase; ANC, absolute neutrophil count; AST, aspartate aminotransferase; ECG, electrocardiogram; LFTs, liver function tests; MOA, mechanism of action; QTcF, corrected QT interval by Fridericia formula; ULN, upper limit of normal

- a These are examples based on previously observed AEs for agents with similar MOA (ie, fostamatinib). All other potential/spontaneous Grade 3/4 AEs that can warrant dose reduction or interruption are not excluded and will be assessed on an ongoing basis during the study. Those would be evaluated upon judgment by the principal investigator and the safety operations team.
- b A central laboratory must be used for repeat ALT, AST, ALP, or ANC.

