### 3.3. Dose Interruption and Reduction

It is recognized that some AEs may require dose adjustment or study drug discontinuation. Intra-patient dose reduction or escalation is permitted and based upon treatment-related adverse events observed. Guidelines for dose interruption or reduction are specified in Protocol Section 3.1.1.

After experiencing an AE, patients whose laboratory results return to baseline values and remain stable for 4 consecutive weeks have the option to increase the dose of SKI-O-703 1 dose level up to the randomized dose level.

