## **9.3. Clinical Laboratory Evaluations**

Clinical laboratory tests will be performed by both central and local laboratory. All summaries will be based on the standard international (SI) units provided by both central and local lab.

The laboratory values will be graded using CTCAE version 5.0. For hematologic and chemistry laboratory values that fall outside of the grade criteria of CTCAE version 5.0, the grade of 0 will be assigned.

Abnormal clinical laboratory values will be flagged as either high or low based on the reference ranges for each laboratory parameter.

Summary statistics of observed values, change and percent changes from baseline in numeric laboratory parameters will be provided by treatment group and combined active treatment group, and scheduled visit indicated in the schedule of events in [Appendix 15.1](#). Numeric values reported as less than (<) or greater than (>) a laboratory-defined limit will be included with the “<” or “>” signs ignored.

For relevant laboratory parameter, frequency summaries of categorical shifts from baseline grade to each post-baseline visit grade, and to the worst post-baseline grade during treatment will be provided in the graded hematology and serum chemistry parameters by treatment group and combined active treatment group.

Line plots of means and SEs will be created to display actual values and change from baseline by scheduled visit.

When there are multiple values within a post-baseline visit for a particular laboratory parameter (except platelet; refer rule of platelet to Section 8), the worst value will be taken (worst being the smallest value for criteria below a certain threshold or the largest value for criteria above a certain threshold). If a patient has a value below the threshold and above the threshold, the value furthest from the threshold will be chosen. If the distances are the same, the value with the recent date/time will be chosen.

All laboratory data will be listed, including unscheduled/repeat visits.

All laboratory data outside the normal range will be listed. For each laboratory test, individual patients with any values outside the standard reference range will have all their test results listed.

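### Protocol Table 1 prints the bilirubin limit for permanent discontinuation in the wrong SI unit: 2 mg/dL is 34.2 micromol/L, not 34.2 mmol/L

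*Protocol*

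**What the plan says.** Table 1 in Protocol Section 3.1.1 sets out what to do after specified adverse events. The row for ALT and alkaline phosphatase elevations ends with a note: "Discontinue study drug permanently if the ALT elevation is accompanied by" a rise in direct bilirubin above a stated limit. The limit is given in two unit systems: "elevation in direct bilirubin to > 2 mg/dL (34.2 mmol/L").

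No other section states this limit in molar units. The eligibility criterion in Protocol Section 4.1.1 (item 5) and the hepatotoxicity event of special interest in Protocol Section 6.4.5.6 both express bilirubin as multiples of the upper limit of normal. SAP Section 3.3 does not restate the rule but refers back to it: "Guidelines for dose interruption or reduction are specified in Protocol Section 3.1.1". SAP Section 9.3 adds, on laboratory data generally: "All summaries will be based on the standard international (SI) units provided by both central and local lab".

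**The concern.** A limit printed in two unit systems should be the same limit in both. Here the second value cannot be a conversion of the first.

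The rule is a stop for liver safety. Protocol Section 1.5 counts liver enzyme changes among the important potential risks, and Section 1.3 says that 400 mg BID had not been given to humans before. Sites are in Korea, the US and the EU (Protocol Section 4.1). The purpose of a dual-unit limit is to spare sites the conversion. If the SI value were copied as printed into a laboratory alert, an eCRF check or a site worksheet, the stop would never trigger. The rule uses direct bilirubin and requires action. The event of special interest in Section 6.4.5.6 uses total bilirubin and governs reporting, so it cannot stand in for this rule.

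**Working it through.** **Inputs**

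- Limit in conventional units: 2 mg/dL (Protocol Section 3.1.1, Table 1).
- Limit in SI units as printed: 34.2 mmol/L (same cell).
- Molar mass of bilirubin: not in the documents. Assumed to be 584.67 g/mol, computed from the formula C33H36N4O6. Because the limit is for direct bilirubin, an assumed 936.9 g/mol for the diglucuronide was tried as well.

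**Step 1: is the printed pair consistent? (no molar mass assumed)**

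2 mg/dL × 10 = 20 mg/L.

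Implied molar mass = mass concentration / molar concentration:

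- As printed: 20 mg/L ÷ 34.2 mmol/L = 0.585 mg/mmol = 0.585 g/mol. A hydrogen atom is about 1 g/mol, so no substance satisfies the pair.
- With micromol/L: 20 mg/L ÷ 0.0342 mmol/L = 584.8 g/mol.

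**Step 2: forward conversion**

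mmol/L = (mg/dL × 10) / molar mass.

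| Assumed molar mass (g/mol) | 2 mg/dL in mmol/L | 2 mg/dL in micromol/L |
|---|---|---|
| 584.67 (bilirubin) | 20/584.67 = 0.0342 | 34.2 |
| 936.9 (diglucuronide) | 20/936.9 = 0.0213 | 21.3 |

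The printed 34.2 mmol/L is not reproduced under either assumption. The numeral 34.2 is reproduced exactly with bilirubin's molar mass, but in micromol/L.

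**Step 3: size of the discrepancy**

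mg/dL = mmol/L × molar mass / 10.

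- At 584.67 g/mol: 34.2 × 584.67 / 10 = 2,000 mg/dL, which is 2,000/2 = 1,000 times the intended limit.
- At 936.9 g/mol: 34.2 × 936.9 / 10 = 3,204 mg/dL, about 1,600 times the intended limit.

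Since 34.2 was evidently obtained with the molar mass of bilirubin itself, 1,000-fold is the relevant figure.

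**The case against.** The strongest reply is that this is a typographical slip with little consequence. The mg/dL value is correct and comes first. A site whose laboratory reports in micromol/L would compare its result with the numeral 34.2 and act correctly. A literal reading gives about 2,000 mg/dL, which is implausible on sight. Other safeguards do not use the SI figure:

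- Table 1 withholds drug when the subject is symptomatic or above 5 × ULN, and stops it permanently at a second occurrence.
- Footnote a describes the table entries as examples and leaves other severe events to the judgment of the principal investigator and the safety team.
- Section 4.2.1 allows withdrawal for clinically significant laboratory changes.
- Section 6.4.4 invokes the FDA guidance on drug-induced liver injury.
- Section 6.4.5.6 defines hepatotoxicity in multiples of ULN.

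All of this stands and limits the severity. It does not make the printed pair consistent, and the note itself is worded as an instruction to stop.

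A second objection is that reading the PDF by program may have turned a micro sign into the letter m. The micro sign comes through correctly in Protocol Sections 3.1, 3.1.2 and 5.8.1, so this is unlikely. Table 1 contains no other micro sign to serve as a control, so it is not fully excluded. A look at the source cell settles it.

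**Conclusion.** The concern holds. The SI value in Table 1 carries the wrong prefix, making the limit as printed about 1,000 times too high. The inconsistency itself needs no outside figure, because the printed pair implies an impossible molar mass. The 1,000-fold size assumes the molar mass of bilirubin. Assuming the diglucuronide instead changes the factor to about 1,600 and leaves the conclusion unchanged. The one remaining doubt is the small chance of a misread character in the table cell.

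The error should be corrected because it sits in a rule for permanent discontinuation and nothing else in the protocol or SAP puts it right. The practical risk is small, and no power calculation, efficacy analysis or SAP summary depends on the figure.

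**What to change.** In Protocol Section 3.1.1, Table 1, replace mmol/L with micromol/L after 34.2, and leave the limit of > 2 mg/dL as it is. If any eCRF check, central laboratory alert or site guide was built from this cell, confirm that it uses micromol/L too.

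The cost is one unit in one table cell. The SAP needs no change, since its Section 3.3 only points to the protocol.
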